- Changes in pain-related symptoms and functioning from baseline as measured by the BPI (which calculates a numeric score) will be compared between treatment groups. As the scientific goal is to demonstrate no worsening of pain, a noninferiority test will compare changes in BPI score between treatment and control groups with a minimal clinically important difference of 1 based on the IMMPACT recommendations. A secondary analysis will distinguish between the effect of STOP on the change in pain-related symptoms for participants with opioid prescriptions at baseline to the effect for those who were enrolled solely due to illicit use.
- Symptoms of depression, suicidality, anxiety, and poor sleep in the past two weeks will be measured at baseline and quarterly (PHQ-8) and at baseline, 6, and 12 months (PROMIS anxiety and sleep measures and PSS), which provide numeric measures. Mean values will be compared between treatment groups.
- Mean values for health-related quality of life scores and COMM scores will be compared between groups.

Similar models will be fit for the Aim 3 objectives, but these will use provider rather than patient as the unit of observation, so will not need a PCP effect to adjust for within-PCP correlation. Regression models will be used to compare number of prescriptions of high-dose opioids within 12 months of follow-up between treatment groups as well as number of days prescribed during 12 months follow-up. Similar analyses will be done for number of prescriptions for any opioids or benzodiazepines, numbers of naloxone kits prescribed, numbers of urine toxicology tests ordered and completed, and number of patient participants receiving a new diagnosis of OUD.

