2.2.2 Secondary Objectives

The trial has two secondary objectives, which capture patient participant-level and provider-level impacts of the STOP intervention.

The patient-level secondary objective (Aim 2) is to examine the impact of STOP on important patient-level outcomes of substance use that increases opioid-related overdose risk (binge alcohol use, benzodiazepine and stimulant use), other drug use, OUD and other drug and alcohol use disorders, overdose risk behaviors and nonfatal overdose events, pain symptoms and related functioning, mental health symptoms (depression, anxiety, suicidality), sleep, health-related quality of life, and acute health care utilization. We hypothesize that patient participants in the STOP condition, in comparison to participants in the EUC condition, will have:

- H2.1 Fewer days of binge alcohol use.
- H2.2 Fewer days of benzodiazepine use.
- H2.3 Fewer days of stimulant use (cocaine and amphetamine-type stimulants).
- H2.4 Fewer days of marijuana use.
- H2.5 Fewer days of other drug use (not including opioids, benzodiazepines, stimulants, and marijuana).
- H2.6 Lower proportion of individuals having increased days of illicit or nonmedical opioid use.
- H2.7 Reduced prescription opioid misuse behaviors, among patients receiving prescribed opioids.
- H2.8 Lower incidence of moderate-severe OUD.
- H2.9 Lower rates of non-opioid drug use disorder or alcohol use disorder.

- H2.10 Lower rates of self-reported overdose risk behavior and nonfatal opioid-related overdose events.
- H2.11 No worsening of pain symptoms and pain-related functioning.
- H2.12 Fewer symptoms of depression (including suicidality) and anxiety.
- H2.13 Better sleep quality.
- H2.14 Better health-related quality of life.
- H2.15 Lower rates of acute health care utilization (ED and hospital visits).

The provider-level secondary objective (Aim 3) is to characterize the impact of STOP on primary care provider behaviors, including medications prescribed, lab tests, diagnosis of OUD, and frequency of medical visits. Our hypothesis is that providers assigned to the STOP condition, in comparison to providers in EUC, will have, over 12 months of follow-up...

- H3.1 Lower rates of prescribing of high-dose opioids (defined as prescriptions totaling >90 morphine milligram equivalents (MME)) to patients with risky opioid use.
- H3.2 Fewer patients with risky opioid use who are prescribed benzodiazepines.

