- H3.3 Higher proportion of patients with risky opioid use receiving at least one prescription for a naloxone kit.
- H3.4 Increased monitoring of patients with risky opioid use, defined as urine drug screen, diagnosis of OUD, and higher visit frequency.

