Measures of provider treatment practices are collected from the EHR at baseline and 12 months, for patient participants. The data extracted for each patient participant will be for the period beginning 12 months prior to study participation, through 12 months following enrollment.

1. H3.1. Prescriptions for opioids: number of patient participants receiving prescriptions for high-dose opioids (>90 MME); moderate-dose opioids (50-90 MME); and any opioids: number of prescriptions; daily prescribed dose; and total number of days prescribed.
2. H3.2. Prescriptions for benzodiazepines: number of patient participants receiving benzodiazepine prescriptions and number receiving both chronic opioid and benzodiazepine prescriptions: number of prescriptions; daily prescribed dose, and total number of days prescribed.

3. H3.3. Prescriptions for naloxone: number of patient participants receiving at least 1 prescription.
4. H3.4. Urine Drug Screens: number ordered and completed for each patient participant.
5. H3.4. Diagnosis of OUD: number of patient participants receiving a new diagnosis of OUD during the study period.
6. H3.4. Primary care visits: number of scheduled visits per patient participant.

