Self-reported overdose risk behavior will be measured by the overdose risk behavior questionnaire (which gives a numeric score) at baseline, 6, and 12 months. Mean scores will be compared between groups at 6 and 12 months in a random-effect regression model. Also, the total number of non-fatal opioid-related overdose events in the past 3 months will be measured at baseline, 6, and 12 months. Mean numbers of opioid-related overdose events will be compared between groups in a random-effect regression model (H 2.10).

Changes in pain-related symptoms and functioning from baseline as measured by the BPI (which calculates a numeric score) will be compared between treatment arms using Mann-Whitney tests. As the scientific goal is to demonstrate no worsening of pain, a noninferiority test will compare changes in BPI score between treatment and control groups with a minimal clinically important difference of 1 based on the IMMPACT recommendations. A secondary analysis will distinguish the effect of STOP on the change in pain-related symptoms for participants with opioid prescriptions at baseline, and the effect for those who were enrolled solely due to illicit use.

Symptoms of depression, suicidality, anxiety (H2.12), and poor sleep (H2.13) in the past two weeks will be measured at baseline and quarterly (PHQ-8) and at baseline, 6, and 12 months (PROMIS anxiety and sleep measures and PSS). Mean values will be compared between treatment arms in random-effect regression models.

Health-related quality of life (H2.14), and ED and hospital utilization (H2.15) in the past two weeks will be measured at baseline and at 6 and 12 months. Mean values will be compared between treatment arms in random-effect regression models.

Similar models will be fit for the Aim 3 objectives, but these will use provider rather than patient as the unit of observation, so will not need a PCP effect to adjust for within-PCP correlation. Regression models will be used to compare number of prescriptions of high-dose opioids within 12 months of follow-up between treatment arms as well as number of days prescribed during 12 months follow-up. Similar analyses will be done for number of prescriptions for any opioids or benzodiazepines, numbers of naloxone kits prescribed, numbers of urine toxicology tests ordered and completed, and number of patient participants receiving a new diagnosis of OUD.

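### Aim 3 tests naloxone kits and benzodiazepine prescriptions, although H3.3 and H3.2 are about patients receiving them, and states no patient denominator for its provider-level counts

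*SAP*

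**What the plan says.** The hypotheses in SAP 2.2.2 are patient-based. H3.2 is "Fewer patients with risky opioid use who are prescribed benzodiazepines" and H3.3 is "Higher proportion of patients with risky opioid use receiving at least one prescription for a naloxone kit". SAP 7.7 defines measures to match: for H3.2 it lists first the "number of patient participants receiving benzodiazepine prescriptions", and for H3.3 the "number of patient participants receiving at least 1 prescription". These data come from the charts of enrolled patients only.

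The Aim 3 paragraph of SAP 7.8 says of its models that "these will use provider rather than patient as the unit of observation, so will not need a PCP effect", and it uses other responses. After high-dose opioid prescriptions and days prescribed, it lists "number of prescriptions for any opioids or benzodiazepines", then "numbers of naloxone kits prescribed, numbers of urine toxicology tests ordered and completed, and number of patient participants receiving a new diagnosis of OUD". Protocol 14.6 opens its paragraph in the same way: "Similar models will be fit for the Aim 3 objectives, but these will use provider rather than patient as the unit of observation". Neither paragraph names an offset, weight or covariate for the number of patients a provider has in the study. Protocol 14.3 expects that number to vary, giving 4, 6 or 10 patients per PCP as one possible pattern.

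**The concern.** There are two separate points.

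**Scale.** A count of kits or prescriptions is the number of recipients multiplied by the mean number per recipient. H3.3 and H3.2 concern only the first factor. An intervention that leads to repeat prescriptions for the same patients would appear to widen coverage. One that widens coverage with fewer items each could appear to do nothing. SAP 7.8 does not explicitly plan a cluster-respecting test of the H3.3 proportion or of the H3.2 patient count.

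**Denominator.** A provider's count rises with the number of that provider's patients in the study. If it is modelled unscaled, variation in patients per PCP adds noise that has nothing to do with prescribing.

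What is at stake is the interpretation of two secondary hypotheses and some precision for the rest of Aim 3.

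**Working it through.** **1. Hypothesis, definition and analysis side by side**

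| | Hypothesis (SAP 2.2.2) | Measure (SAP 7.7) | Response (SAP 7.8, Protocol 14.6) |
|---|---|---|---|
| H3.2 | patients on benzodiazepines | patients; prescriptions also listed | prescriptions only |
| H3.3 | proportion of patients with naloxone | patients with one or more prescriptions | kits |
| H3.4, new OUD diagnosis | diagnosis as part of monitoring | patients | patients, no denominator stated |
| H3.4, urine screens | testing | per patient | tests, no denominator stated |

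Prescription counts and days prescribed also appear in SAP 7.7, so for H3.1 the response and the definition agree.

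**2. What the scale change can do.** The documents give no Aim 3 event rates, so these are assumed. Kits per patient = proportion covered × kits per recipient.

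- Equal coverage: EUC 0.30 × 1.2 = 0.36; STOP 0.30 × 1.8 = 0.54. Kit ratio 0.54/0.36 = 1.5; proportion ratio 0.30/0.30 = 1.0.
- Unequal coverage: EUC 0.30 × 1.5 = 0.45; STOP 0.45 × 1.0 = 0.45. Kit ratio 1.0; proportion ratio 0.45/0.30 = 1.5.

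The equal-coverage case was simulated with 31 PCPs per arm, between-PCP log-variance 0.15 (borrowed from the power simulation in SAP 10.0), 1 + Poisson kits per recipient, a log-link model with PCP-level robust standard errors, no baseline term and a two-sided 5% test. The kit comparison was significant in about 37% of trials and the patient proportion in about 5%. An offset alone does not cure this, because 0.36 and 0.54 are already per-patient figures.

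**3. Cluster sizes.** The protocol's pattern reproduces its total: 50×4 + 5×6 + 7×10 = 300 patients in 62 PCPs. Writing m for patients per PCP: E(m) = 300/62 = 4.84; E(m²) = 1680/62 = 27.10; Var(m) = 27.10 − 4.84² = 3.68; CV = 0.40.

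**4. Precision lost if counts are unscaled and unadjusted for baseline.** If m is unrelated to the prescribing rate,

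SE ratio (unscaled : offset) = √(1 + Var(m)/D)

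- for μ events per patient (Poisson), D = E(m)/μ + E(m²)(e^0.15 − 1);
- for a yes/no outcome with probability p, D = E(m)/p − E(m)·e^0.15 + E(m²)(e^0.15 − 1).

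Here e^0.15 − 1 = 0.162, so the last term is 4.39 throughout.

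| Assumed outcome | D | Formula | Simulation |
|---|---|---|---|
| yes/no, 10% | 47.15 | 1.04 | 1.04–1.05 |
| yes/no, 30% | 14.89 | 1.12 | 1.11–1.13 |
| one event per patient | 9.22 | 1.18 | 1.17–1.19 |
| three events per patient | 6.00 | 1.27 | 1.25–1.26 |

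Opioid prescriptions, with 17.5% of patients on opioids (the middle of the 15–20% in Protocol 14.3) and an assumed 12 prescriptions a year each, gave 1.04–1.05 in simulation.

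With both models adjusted for the pre-enrolment measure, the simulated ratio was 1.00–1.11. The upper end includes a measure that is rare before enrolment (3% before, 30% after), as naloxone may be. At exactly five patients per PCP, Var(m) = 0 and the ratio is 1.00.

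**The case against.** - **Counts are not foreign to the plan.** SAP 7.7 lists benzodiazepine prescriptions as a sub-measure, and the protocol synopsis speaks loosely of more naloxone prescribing. That stands, and is a reason to report the counts. It does not make them the test of hypotheses worded in patients. Protocol 11.5.12 lists only a date for each naloxone prescription, so kits may in practice mean prescriptions; repeat prescriptions raise the same problem.
- **SAP 7.8 has a general sentence** offering chi-square tests for categorical secondary outcomes. It sits with the COMM score analysis for H2.7 and ignores clustering, so it does not supply the missing H3.3 or H3.2 analysis.
- **The scale effect needs kits per recipient to differ by arm.** This is correct for false signals, and the documents give no such figures. With equal kits per recipient (1.2) and coverage of 30% vs 45%, counting kits costs only about 4 to 6 points of power.
- **The text does not say unscaled totals.** A provider-level mean per patient would also fit it. A reader might infer that the plan has chosen raw totals; what the documents show is that the denominator is left unstated.
- **Biased ratios.** A reader might infer that the Aim 3 ratios will be biased because PCPs know their arm and patients enrol after randomisation. That needs enrolment per PCP to differ by arm. No such difference is documented, staff try to reach all adult patients of participating PCPs (Protocol 8.2.2), and patients per cluster are to be tabulated by arm (SAP 4.1.1).
- **Visit frequency.** A reader might infer that this part of H3.4 has no analysis. SAP 7.10 models visits attended and scheduled visits missed by PCP, which covers most of it; the link to H3.4 is what is missing.

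**Conclusion.** The mismatch for H3.3 and H3.2 stands on the text alone: followed as written, the Aim 3 paragraph tests a different quantity from the one hypothesised and defined. How far the two could diverge depends on kits or prescriptions per recipient, which is unknown. The 37% against 5% contrast illustrates one assumed pattern and is not a forecast.

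The unstated denominator is a smaller matter. It costs precision only if unscaled counts are modelled and patients per PCP vary. The ratios in the working rest on assumed event rates, the protocol's 4/6/10 pattern and a borrowed between-PCP variance. The words similar models may carry over site and baseline terms, but no model in the SAP has a patients-per-PCP term to carry over.

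Using the provider as the unit is not itself the fault, provided that the unit is the randomised PCP or team, as SAP 7.2.2 already requires for the primary outcome. These are secondary outcomes without multiplicity adjustment, and the primary result is unaffected.

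**What to change.** Amend the Aim 3 paragraph in SAP 7.8 and Protocol 14.6 as follows.

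1. **Unit:** the randomised PCP or PCP team, as in SAP 7.2.2, with at least one enrolled patient (the SAP 3.1.3 population).
2. **Patient-based measures:** analyse H3.3 (at least one naloxone prescription), H3.2 (any benzodiazepine prescription) and new OUD diagnosis as n of N patients per cluster, in a binomial model with robust standard errors or a scale parameter.
3. **Counts:** for prescriptions, days prescribed and urine tests, add an offset of log(patients with abstracted charts). Abstracted is safer than enrolled, because SAP 3.2.5 notes that some charts are not abstracted.
4. **Adjustment:** state site and the same measure in the 12 months before enrolment for all of these models.
5. **Descriptive additions:** report naloxone kit and benzodiazepine prescription counts alongside.
6. **Visits:** state that the SAP 7.10 visit analysis serves H3.4, with the same offset.

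The offset corrects for patient numbers, not for patient mix. The cost is SAP and protocol wording plus minor programming. Patients per cluster, abstraction status and 12 months of pre-enrolment chart data are already collected.

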7.9 Definition of the Exploratory Outcome Measures

The following additional measures will be collected to assess exploratory outcomes, characterize domains from conceptual models, and may be used to adjust models of the primary and secondary outcomes. These measures are collected at the baseline study visit and at the study visits specified in Tables 5 and 6 (schedule of assessments) in the protocol.

1. Patient engagement in primary care (Exploratory Objective 1): Number and frequency of kept appointments and missed appointments for primary care visits.
2. Time to development of moderate-severe OUD or opioid related overdose for participants in both treatment conditions (Exploratory Objective 2).
3. Overdose death is expected to be a rare event in this population (Exploratory Objective 3) and will be assessed from the EHR and from other administrative data kept by the health system or government entities, for participants who cannot be reached at the time of the 12-month study visit.
4. Addiction treatment and harm reduction program utilization (Exploratory Objective 4): Self-reported number of weeks of addiction treatment or harm reduction program services, and self-reported number of weeks receiving MOUD is assessed at baseline and at 6 and 12 months. Prescriptions for MOUD received in the primary care clinic are additionally assessed from the EHR from at 12 months.
5. TLFB measure of substance use in the past 90 days (Exploratory Objective 5): A 90-day TLFB administered at the 3- and 6-month quarterly assessments, will capture days of risky opioid use, binge alcohol use, and other drug use including benzodiazepines, cocaine, stimulants, marijuana, and other drugs. For any prescription opioids, benzodiazepines, and amphetamine-type stimulants, the TLFB will measure non-medical use.
6. Frequency of PCP counseling on opioid use (Exploratory Objective 6): For patient participants who have a PCP encounter integrated with the baseline research visit, counseling is measured with the baseline exit survey. For all patient participants, information on any discussion or counseling provided during follow-up PCP encounters will be assessed with a quarterly patient experience questionnaire.

Other exploratory outcomes listed in the protocol included:

7. Patient participants' self-assessments of readiness to change risky opioid use and other substance use will be measured using two items that query self-reported readiness and confidence to change, rated on a 10-point scale.
8. Social support will be assessed using the PROMIS instrumental and emotional health short forms.
9. PCP knowledge and attitudes regarding substance use, subthreshold OUD, and opioid management, assessed at baseline and at the end of the intervention period.

7.10 Analyses of the Exploratory Outcome Measures

The LN will analyze all exploratory outcomes. For the exploratory objectives, regression models with PCP as the unit of observation will compare the mean number of primary care visits attended and number of scheduled visits missed between treatment arms over the 12-month follow-up period. Time-to-event analysis will be used to compare time to development of moderate to severe OUD between treatment arms. Proportions of fatal overdose deaths will be presented by treatment arm with 95% confidence intervals. TLFB results will be described and examined alongside the days of substance use reported in the monthly assessments, in order to describe the consistency of results with these two measurement approaches. Proportions of PCP visits with counseling on risks of opioid use will be compared between groups. For PCP knowledge and

attitudes, analyses will describe and compare responses at baseline and end of intervention, for PCPs assigned to the intervention versus control condition.

8.0 SAFETY OUTCOMES AND ANALYSIS

Because this is a minimal risk study with no pharmacological intervention, causally related Adverse Events and Serious Adverse events are not anticipated for this study. Collection and reporting of Adverse Events and Serious Adverse Events is not required in the data system.

Safety reporting will be limited to reporting the following Safety Events: non-fatal alcohol or drug overdose events, suicidal ideation, hospitalizations, emergency department (ED) visits, and deaths.

The safety population will be used for reporting Safety Events.

8.1 Non-fatal Drug or Alcohol Overdoses

The number of patient participant self-reported non-fatal drug or alcohol overdoses in the past 6 months is collected at baseline, 6-months, and 12-months. A non-fatal drug or alcohol overdose is defined as taking too many drugs and/or medications/pills, or drinking too much alcohol, which causes 'poisoning', 'passing out', 'nodding out', 'blacking out', or an 'overdose' or 'OD'.

A summary table of the total number of self-reported non-fatal overdoses, number of patient participants reporting at least one non-fatal overdose as well as the number of non-fatal overdoses reported per patient participant at each visit will be presented by treatment arm. A listing of the number of overdoses reported at each visit for patient participants who have reported at least one overdose at any visit by treatment arm will be provided. The listing will include Site, Participant ID, date of enrollment, visit, date of assessment, number of overdoses, and comments from the Non-Fatal Overdose Questionnaire (NFO).

8.2 Suicide Risk

The questions 'Over the past 2 weeks, have you had thoughts of killing yourself?' and 'Have you ever attempted to kill yourself? If yes, when did this last happen?' are asked on the Patient Safety Screener (PSS) assessment at baseline, 6-months, and 12-months. A response of 'yes' to having suicidal thoughts over the last 2 weeks or 'yes' to attempting suicide within the last 24 hours (including today) or within the last month (but not today) indicates potential suicide risk.

A summary table of the number of patient participants endorsing suicidal ideation at baseline, 6-months, and 12-months, as well as the number of patient participant endorsing suicidality at either 6 or 12-months, will be presented by treatment arm. A listing for all visits for patient participants endorsing suicidality at least one visit will be presented by treatment arm. The listing will include Site, Participant ID, date of enrollment, visit, date of assessment, and the questions 'Over the past 2 weeks, have you had thoughts of killing yourself?' and 'Have you ever attempted to kill yourself? If yes, when did this last happen?' from the PSS assessment.

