11.5.8 Depression and Suicidality (PHQ-8 and PSS)

Assessment of depression symptoms and suicidality is accomplished with the Patient Health Questionnaire (PHQ-8) depression screening tool, and the Patient Safety Screener (PSS). The ninth item of the PHQ-9 is about suicidal ideation, which is queried separately in our study as part of the PSS. The PHQ-8 has been validated as a measure of depression, independent of the PHQ-9.[66] The PSS is a validated screening instrument that was used in the ED-SAFE study. It consists of one item about suicidal ideation in the past two weeks, followed by one item about lifetime suicide attempts, in a yes/no format. Individuals reporting a suicide attempt are asked when this last occurred. The PSS is administered by research staff for safety reasons, to allow for rapid assessment and response for patients with suicidality (following safety procedures specified in the site’s standard operating procedures).

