	Number of participants with at least one non-fatal drug or alcohol overdose	N (X.X%)		
	Number of non-fatal drug or alcohol overdoses per participant			
	N	N		
	Mean	X.X		
	SD	X.XX		
	Minimum	X		
	Median	X.X		
	Maximum	X		

Table 66: Summary of Suicide Risk by Treatment Arm Patient Participants			
	Treatment Arm		Total (N=)
	EUC (N=)	STOP (N=)	
Number endorsing suicide risk on PSS ¹ at Baseline	N (X.X%)		
Number endorsing suicide risk on PSS at 6-months	N (X.X%)		
Number endorsing suicide risk on PSS at 12-months	N (X.X%)		
Number endorsing suicide risk on PSS at either 6 or 12-months	N (X.X%)		

¹ Patient Safety Screener. PSS is administered at baseline, 6-months, and 12-months. Endorsing suicide risk on PSS is defined as a response of 'yes' to having thoughts of killing themselves over the last 2 weeks or if they attempted to kill themselves within the last 24 hours (including today) or within the last month (but not today).

Table 67: Summary of Hospitalizations by Treatment Arm				
Patient Participants				
Visit		Treatment Arm		
		EUC (N=)	STOP (N=)	Total (N=)
6-month	Number of hospitalizations	N		
	Numbers of participants with hospitalizations	N (X.X%)		
	Number of hospitalizations per participant			
	0	N (X.X%)		
	1			
	2			
	3			
	4			
	5 or more			
	Number of hospitalizations per participant			
	N	N		
	Mean	X.X		
	SD	X.XX		
	Minimum	X		
	Median	X.X		
	Maximum	X		
12-month	Number of hospitalizations	N		
	Numbers of participants with hospitalizations	N (X.X%)		
	Number of hospitalizations per participant			
	0	N (X.X%)		
	1			
	2			
	3			
	4			
	5 or more			
	Number of hospitalizations per participant			
	N	N		
	Mean	X.X		
	SD	X.XX		
	Minimum	X		
	Median	X.X		
	Maximum	X		

Table 68: Summary of ED Visits by Treatment Arm				
Patient Participants		Treatment Arm		
Visit		EUC (N=)	STOP (N=)	Total (N=)
6-month	Number of ED visits	N		
	Numbers of participants with ED visits	N (X.X%)		
	Number of ED visits per participant			
	0	N (X.X%)		
	1			
	2			
	3			
	4			
	5 or more			
	Number of ED visits per participant			
	N	N		
	Mean	X.X		
	SD	X.XX		
	Minimum	X		
	Median	X.X		
	Maximum	X		
12-month	Number of ED visits	N		
	Numbers of participants with ED visits	N (X.X%)		
	Number of ED visits per participant			
	0	N (X.X%)		
	1			
	2			
	3			
	4			
	5 or more			
	Number of ED visits per participant			
	N	N		
	Mean	X.X		
	SD	X.XX		
	Minimum	X		
	Median	X.X		
	Maximum	X		

Listing 1: Listing of Non-fatal Drug or Alcohol Overdoses by Treatment Arm						

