Patient Participants						
Treatment Arm = EUC/STOP						
Site	Participant ID	Date of Enrollment	Visit	Date of Assessment	Number of Overdoses¹	Comments
xxxxxxxxxx	xxxxxxxxxxxxxx	mm/dd/yyyy	Baseline/ 6-month/ 12-month	mm/dd/yyyy	N	xxxxxxxxxx

¹ Only the number of non-fatal drug or alcohol overdoses in the past 6 months are reported at each visit.

Listing 2: Listing of Suicide Risk by Treatment Arm							
Treatment Arm = EUC/STOP							
Site	Participant ID	Date of Enrollment	Visit	Date of Assessment	Over the past 2 weeks, have you had thoughts of killing yourself?	Have you ever attempted to kill yourself?	If yes, when did this last happen?
xxxxxxxxxx	xxxxxxxxxxxxxx	mm/dd/yyyy	Baseline/ 6-month/ 12-month	mm/dd/yyyy	Yes/ No/ Unable to complete	Yes/ No	Within the last 24 hours (including today)/ Within the last month (but not today)/ Between 1 and 6 months ago/ More than 6 months ago

All visits are included for participants who answered 'yes' to having thoughts of killing themselves over the last 2 weeks or if they attempted to kill themselves within the last 24 hours (including today) or within the last month (but not today).

Listing 3: Listing of Hospitalizations by Treatment Arm
Patient Participants

Treatment Arm = EUC/STOP

Site	Participant ID	Treatment Arm = EUC/STOP					Severity	Outcome
		Date of Enrollment	Date of Hospitalization	Date of Discharge	Primary Diagnosis/ Complaint	Secondary Diagnosis/ Complaint	Tertiary Diagnosis/ Complaint	
xxxxxxxxxx	xxxxxxxxxxxx	mm/dd/yyyy	mm/dd/yyyy	mm/dd/yyyy	xxxxxxxxxx	xxxxxxxxxx	xxxxxxxxxx	Recovering/resolving/ Recovered/resolved/ Recovered/recovered with sequela/ Not recovered/not resolved/ Fatal/ Unknown

All hospitalizations are as reported on the ED Visits and Hospitalization (EDH) form.

Listing 4: Listing of ED Visits by Treatment Arm
Patient Participants

Treatment Arm = EUC/STOP						
Site	Participant ID	Date of Enrollment	Date of ED Visit	Date of Discharge	Primary Diagnosis/ Complaint	Secondary Diagnosis/ Complaint
xxxxxxxxxx	xxxxxxxxxxxxxx	mm/dd/yyyy	mm/dd/yyyy	xxxxxx	xxxxxxxxxx	xxxxxxxxxx

All ED visits are as reported on the ED Visits and Hospitalization (EDH) form.

Treatment Arm = EUC/STOP							MedDRA vxx.x	
Site	Participant ID	Date of Enrollment	Date of Death	Source of Death Report	Type	Cause of Death	MedDRA vxx.x	
							Preferred Term	System Organ Class

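### The suicide-risk table counts an attempt only if it fell in the month before a PSS visit, so a follow-up attempt reported as one to six months old is collected but does not by itself count

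*SAP*

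**What the plan says.** SAP 8.2 places the PSS "assessment at baseline, 6-months, and 12-months". Two answers mark a participant as at risk. The first is "A response of 'yes' to having suicidal thoughts over the last 2 weeks". The second is a yes to "attempting suicide within the last 24 hours (including today) or within the last month (but not today) indicates potential suicide risk".

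The footnote to Table 66 repeats the rule: thoughts in the last two weeks, or "if they attempted to kill themselves within the last 24 hours (including today) or within the last month (but not today". The table gives the number meeting it, by arm, at each visit, and ends with the row "Number endorsing suicide risk on PSS at either 6 or 12-months". It has no row for attempts and none for ideation alone.

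Protocol 11.5.8 describes the attempt item as covering lifetime attempts, and adds: "Individuals reporting a suicide attempt are asked when this last occurred". The Listing 2 shell shows the answer bands. After the 24-hour band come "Within the last month (but not today)/ Between 1 and 6 months ago/ More than 6 months ago". Listing 2 prints every visit, with the band, but only for participants who meet the Table 66 rule at one or more visits.

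**The concern.** The rule suits a screen for current risk on the day of a visit. Here it also supplies the only by-arm summary of suicidality in the safety section, over visits six months apart. The look-back for attempts is one month, so most of each interval lies outside it, even though the form records a band that would cover the rest.

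The SAP's other safety sections leave no such hole. Non-fatal overdoses (8.1) are asked about with a six-month look-back at the same visits. Hospitalizations and ED visits (8.3, 8.4) cover all post-baseline time, as recorded by staff. Deaths (8.5) are listed.

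What is at stake is the completeness of a safety summary in a trial that limits safety reporting to five event types and does not require adverse events in the data system (Protocol 15.16.3; SAP 8.0). A reader of Table 66 could take a zero for attempts during follow-up when the database holds some.

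**Working it through.** The plan gives no figure on this point, so there is none to reproduce. The check sets the counting rule against the form and then counts days.

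**Inputs**
- PSS visits: baseline, 6 and 12 months (SAP 8.2).
- Study month: 30 days (SAP 3.3.3), so the follow-up visits fall at days 180 and 360.
- Attempt look-back that counts: the 24-hour and last-month bands together, taken as 30 days.
- Visit window for the PSS: 1 week early to 3 weeks late (Protocol Table 6).

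**One participant followed through the rule.** Suppose an attempt on day 90 and no suicidal thoughts in the two weeks before any visit.
- Day 180: the attempt is 180 − 90 = 90 days old, in the one-to-six-month band. Not counted.
- Day 360: it is 360 − 90 = 270 days old, in the over-six-months band. Not counted.
- Unless the baseline answers met the rule, this participant is in neither Table 66 nor Listing 2, although the form recorded the attempt.

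**Share of follow-up time in which an attempt counts**
- Counted: 2 visits × 30 days = 60 days; 60 / 360 = 16.7%.
- Not counted: 360 − 60 = 300 days; 300 / 360 = 83.3%, that is months 1–5 and 7–11.

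**How far this moves**
- Month of 28 days: 56 / 360 = 15.6%. Month of 31 days: 62 / 360 = 17.2%.
- 12-month visit one week early (day 353): 60 / 353 = 17.0%. Three weeks late (day 381): 60 / 381 = 15.7%. Moving the 6-month visit within its window does not change these.
- One of the two visits missed: 30 / 360 = 8.3%.

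**With the one-to-six-month band included.** Taking six months as 180 days, 2 × 180 = 360 of 360 days, if both visits are held on target. Off target, coverage is imperfect:
- 6-month visit at day 173: the look-back starts 180 − 173 = 7 days before baseline.
- 6-month visit at day 201: it starts at day 201 − 180 = 21, so the first three weeks are missed.
- Visits at days 201 and 353: the second look-back starts at day 353 − 180 = 173, an overlap of 201 − 173 = 28 days in which one attempt could be reported twice.
- Visits at days 173 and 381: the second look-back starts at day 381 − 180 = 201, leaving a gap of 201 − 173 = 28 days.

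**The case against.** The strongest reply is that Table 66 delivers what it defines. The declared Safety Event is suicidal ideation, not attempt (Protocol 15.16; SAP 3.3.5 and 8.0), and section 8.2 defines risk at a visit. On that view the point asks for an extra output and exposes no error. This does not dispose of it. The SAP's own rule already counts recent attempts, and its text describes the combined 6- or 12-month figure as suicidality. Having brought attempts in, it then leaves out most of the interval for which they are recorded.

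Other parts of the reply stand:
- A participant with ideation in the two weeks before a visit is counted whatever the date of the attempt.
- An attempt by overdose may appear in the six-month overdose count. One that led to acute care and came to staff attention may appear in the ED or hospitalization outputs with its diagnosis. A fatal one would be in the death listing and narratives. None of these gives a labelled count of attempts by arm, and an attempt with neither overdose nor medical contact would appear in none of them.
- PSS suicidality is also a secondary outcome (H2.12). SAP 7.8 describes those symptoms as past-two-week, so that analysis does not clearly pick up the older band.
- Table 66 is descriptive, the primary analysis does not use it, and the data are kept.

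A reader might go further and infer that 83% of on-study attempts are missed, or that the safety outputs are blind to attempts. The documents support neither. The 83% is a share of days, no attempt rate or timing is given, and the routes above exist.

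**Conclusion.** The gap is real and lies in the tabulation, not in data collection. Followed as written, SAP 8.2, Table 66 and Listing 2 leave out an attempt reported at month 6 or 12 as one to six months old, unless the participant qualifies in some other way.

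The counted attempt look-back is about 60 of 360 follow-up days (17%), assuming 30-day months and both visits completed. It is 15.6% to 17.2% under the month lengths and visit windows tried, and 8.3% if one visit is missed. It equals a share of attempts only if attempts are spread evenly over follow-up and the participants concerned have no ideation in the two weeks before a visit. The documents establish neither condition.

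This is a worthwhile, inexpensive improvement to a safety summary. It is not a must-fix: no test, and nothing in the primary analysis, depends on the table.

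**What to change.** In SAP 8.2 and Table 66:
- Keep the existing suicide-risk rows.
- Show past-two-week ideation as its own row.
- Add a participant-level row, *suicide attempt reported within the past 6 months*, at 6 months, 12 months and either visit. It takes the 24-hour, last-month and one-to-six-month bands together. Count each participant once in the either-visit row, which also deals with overlapping look-backs.

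The label should not say *since the previous PSS*. The bands do not match that interval when visits are early, late or missed.

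In Listing 2, extend the filter to these participants.

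Add footnotes stating that:
- only the most recent attempt is recorded;
- early or late visits can bring in a few pre-baseline days, miss the first weeks of follow-up or leave a short gap between look-backs, to be checked against the baseline PSS and the assessment dates;
- if the 6-month PSS is missed, the over-six-months band at month 12 mixes early on-study attempts with pre-baseline ones. Comparison with the baseline PSS separates them where no lifetime attempt was reported at baseline; otherwise they may stay ambiguous.

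The cost is a paragraph of SAP text, two kinds of table row, one listing filter and the footnotes. The answers are already on the PSS form, and nothing about visits or data collection changes.
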